9.8.2 Research biopsy

A pre-treatment tumor biopsy will be obtained at the time of ablation or fiducial placement or during a separate procedure. On treatment biopsies will be performed 1 week (±3 days) after completing RT or undergoing ablation (from the radiated/ ablated lesion), and then 4 weeks (±1

week) after dose #1 of pembrolizumab (from a non-radiated/ ablated lesion). For patients that are unable to have biopsy 4 weeks after dose #1 of pembrolizumab, the procedure may be delayed up until Week 9.

Patients will be permitted to continue enrollment and treatment on protocol in the event that insufficient material was obtained from the biopsy. The on treatment biopsy will not be required if this is no longer considered appropriate at the time of the planned procedure, for example, if the tumor is no longer accessible or the procedure is deemed to be unsafe. Tumor lesion planned for on-treatment biopsy may be an index lesion if ≥ 2 cm in at least one diameter.

If clinically practical, subjects will undergo up to 5 core biopsies. Three core biopsies will be placed in formalin and processed for FFPE, 2 core biopsies will be immediately frozen in liquid nitrogen and then stored at -80°C (appendix B). All tissue obtained during biopsy procedures will be sent to the IMF facility for analysis under this study as indicated below. If the patient undergoes a routine procedure, tissue may be obtained for future correlative analyses. Up to 20 x 5μ m slides (unstained) may be obtained from each routine procedure where tissue was extracted. Tissue from routine procedures may be sent directly to the IMF facility for immediate processing (e.g. isolation of Tumor Infiltrating Lymphocytes).

9.8.3 Correlative studies

Pharmacodynamic changes may be evaluated for associations with clinical activity, and safety (adverse event) data. Tissue may be used for correlative studies such as IHC, tumor mutation analysis, proteomic analysis, and immunodiversity. PDL-1 immunohistochemistry will be done by a Merck designated laboratory. Other assessment will be done at MSKCC.

9.8.3.1 Whole Blood

Flow cytometry will be performed at baseline and during treatment to assess baseline and changes in composition/activation status of lymphocyte subsets present in peripheral blood mononuclear cell preparations (PBMCs). Lymphocyte subsets to be assayed may include, but are not limited to CD8+ and CD4+ T-cell subsets (activated; effector/memory; regulatory) and populations of those cells as defined by the expression of activation, exhaustion, or signaling markers such as ICOS, HLA-DR, PD-1, CTLA-4, and/or intracellular IFNy. NK cell populations may be monitored in a similar fashion with a focus on characterizing subsets defined by the expression of activation markers (e.g. NKG2D; IL-21R) and/or by markers that are associated with the potential of NK cells to lyse target cells (e.g., CD107a, granzyme, perforin). Additional flow cytometry-based assays will focus on defining and monitoring the abundance of myeloidderived suppressor cells (MDSCs), a cell type which appears to negatively impact anti-tumor activity and which has been shown to promote immune escape by limiting activated CD8 T-cell infiltration into the tumor microenvironment [17]. Immune cells may be evaluated using HLA-A2restricted tetramer assays to detect and quantify the presence of T cells directed against specific antigens which are anticipated to be presented to the immune system due to study treatment. Detecting on-treatment increases in these T cell populations may be considered evidence of adaptive immune responses in CRC.

9.8.3.2 Plasma

To understand the prevalence of circulating proteins and the impact they may have on the clinical activity and/or safety of pembrolizumab treatment, the protein concentrations of a panel

of cytokines, chemokines, and other relevant immunomodulatory, soluble factors may be investigated by ELISA and/or other relevant multiplex-based protein assay methods. Examples of analytes to be assessed may include but are not limited to factors induced by IFNγ signaling (e.g., T cell chemoattractants CXCL9; CXCL10) and other factors generally involved in inflammatory processes. Plasma may be used also to assess the presence and/or concentration of anti-tumor antibodies using a mulitplex platform such as Invitrogen"s Protoarray platform(c). Levels of sPD-L1 in peripheral blood may also be assessed.

9.8.3.3 Tissue Biopsies and/or archived tissue

The presence of TILs within tumors in response to pembrolizumab treatment will be evaluated baseline and on-treatment biopsies and, when feasible, tissue acquired from routine procedures. Archived tissue (up to 20 x 5 μ m slides), tissue acquired from routine procedures (up to 20 x 5 μ m slides per procedure), and biopsy tissue may be analyzed using immunohistochemistry for PD-L1 expression and other immune-related genes, and gene expression (microarray and/or RT- QPCR) research platforms. Laser Capture Microdissection may be utilized to enrich specific regions of tumor material for use in similar or additional downstream applications, which may include in-situ hybridization, flow cytometry, ELISA, and/or assessment of miRNA. In all cases, the goal may be to determine the abundance of a battery of immunoregulatory genes or proteins associated with cancer cells and/or cancer-interacting lymphocytes derived from biopsied material. Other biomarkers may be evaluated as determined by additional data. Remaining specimens may be stored for future studies related to CRC immunity.

10.0 EVALUATION DURING TREATMENT/INTERVENTION

Study Calendar

Period	Screening						Trea	tment			End of
Cycle ¹	4C	1	1	2	2	3	4	5	6	7+	study
Week	<6 weeks ²	0	1	3	4	6	9	12	15	18+	visit ¹⁵
Informed consent	Х										
Medical history	Х										
EKG	Х										
CT/MRI ³	х						х			х	х
Height ⁴	Х										
Physical examination	Х	Х		Х		Х	Х	Х	Х	х	Х
Vital signs/ Performance status ⁴	Х	х		х		Х	Х	Х	Х	х	х
Report medications	Х	х		х		Х	Х	х	Х	х	х
Pulse oximetry		Х		Х		Х	Х	Х	Х	х	Х
Report side effects				х		Х	Х	Х	Х	х	Х
CBC ^{5,6}	Х	Х		х		Х	Х	Х	Х	х	Х
Comp ^{5,7}	Х			х		Х	Х	Х	Х	х	Х
Thyroid function (TSH, fT3,fT4)	х					х		х		odd cycles	
CEA ⁸	х	х					х			х	х
Hepatitis B and C ⁹	Х										
Pregnancy test if female (Serum) ¹⁰	Х										
Research blood tests 5,11	Х			х		Х	Х				
Obtain archived tissue ¹²	Х										
Research tumor biopsy ¹³	Х		Х		х						
RT (Cohort 1) ¹⁴	Х										
Ablation (Cohort 2) ¹⁴	Х										
Pembrolizumab		х		х		х	х	х	х	х	

- 1. Each cycle is approximately 3 weeks in duration, corresponds to 1 completed treatment.
- 2. Procedures must be performed within 6 weeks prior to dose 1 of Pembrolizumab on Day 1.
- 3. CT or MRI will be performed during screening, then at 9 week (±1 wk) intervals and at final visit if more than 4 weeks from prior imaging. If patient is unable to receive CT contrast or the abdominal/ pelvic target lesion is indeterminate on CT then MRI with contrast (abdomen and pelvis) plus CT without contrast (chest) may be performed. Imaging may be delayed up to 2 weeks if patient is receiving additional RT or ablation.
- 4. Vital signs to include heart rate, respiratory rate, blood pressure, and weight.
- 5. Blood to be collected prior to dosing any study medications.
- 6. Hematology to include standard complete blood cell (CBC) panel.
- 7. Comprehensive metabolic panel included sodium, potassium, chloride, bicarbonate, BUN, creatinine, glucose, total protein, albumin, bilirubin, alkaline phosphatase, AST, ALT, calcium.
- 8. CEA to be obtained during screening, day 1 and then within two weeks (or on day) of subsequent imaging.
- 9. Serology for HepBsAg, HepBcAb and hepatitis C antibody (unless previously tested negative).
- 10. Serum pregnancy test is required within 2 weeks of starting radiation or ablation
- 11. Blood draws for research purposes performed during screening or day 1, then weeks 3, 6 and 9 for all patients. Additional blood draws beyond week 9 are permitted based upon interesting clinic/immunological findings for all patients.

- 12. Up to 20 x 5µm slides (unstained) of archived tissue will be requested on all patients for research purposes. For patients undergoing routine procedures during the study, additional tissue (up to 20 x 5µm slides (unstained)) may be obtained from each routine procedure. for research purposes.
- 13. Research tumor biopsy will be performed during fiducal placement or ablation or during a separate procedure, then 1 week (±3 days) after completing RT or ablation (from the radiated/ablated lesion) and 4 weeks after dose #1 of pembrolizumab (±1 week) from a non-ablated/radiated lesion. For patients that are unable to have biopsy 4 weeks after dose #1 of pembrolizumab, the procedure may be delayed up until Week 9.
- 14. RT begins or ablation is performed during cycle 1, within one week prior to dose 1 of Pembrolizumab.
- 15. EOS visit occurs 4(±1 wk) weeks after last dose of pembrolizumab. CT scan or MRI to be done only if last imaging was conducted greater than four weeks prior to the date of the Final Visit.

11.0 TOXICITIES/SIDE EFFECTS

The most commonly reported treatment emergent AEs related to pembrolizumab are fatigue (43.8%), nausea (26.7%), cough (25.3%), pruritus (24.6%), diarrhea (22.3%) and rash (21.5%). Immune-related adverse events were reported in 21.4% of melanoma patients; most of these events (15.8%) were considered drug-related by the investigator. The most commonly reported, immune-related adverse events across the dose-schedules are rash (3.2%), pruritus (2.9%), vitiligo (2.9%), hypothyroidism (2.7%), arthralgia (2.2%), diarrhea (2.2%), and pneumonitis (1.9%).

11.1 SAFETY MONITORING

Subjects will be evaluated for occurrence of AEs at each visit. Events will be characterized and reported as described below. Safety will also be monitored by performing physical exams and routine laboratory procedures.

11.1.1 Adverse Events and Serious Adverse Events

Definitions of AEs, non-serious AE, and serious adverse events (SAEs) are provided in this section. Additionally, provided in the sections below are reporting guidelines for any AE or SAE occurring during this study.

Definition of Adverse Event and Non-Serious Adverse Event

The following definition of AE will be used for the study: "Any untoward medical occurrence in a subject or clinical investigation subject administered a pharmaceutical product and which does not necessarily have to have a causal relationship with this treatment. An adverse event can therefore be any unfavorable and unintended sign (including an abnormal laboratory finding), symptom, or disease temporally associated with the use of a medicinal (investigational) product, whether or not related to medicinal (investigational) product."

This definition includes any abnormalities or anomalies that were not seen at baseline or which worsened during the course of the study, if present at baseline.

A "non-serious" adverse event is any event that does not meet the definition of "serious adverse event" as presented, below.

Reporting and Treating Non-Serious Events

It is the responsibility of the investigator to perform regular assessments for AEs. Subjects will be regularly queried about the occurrence of any AEs and will be monitored throughout the

study for reactions to study drug and/or study procedures. The investigator and clinical staff will record all AEs, whether volunteered by or elicited from the subject, at any time during a subject"s participation in the study. Abnormal laboratory findings (e.g., hematology, comprehensive metabolic panel) or other abnormal assessments (e.g., vital signs) will be recorded as AEs if they are judged as clinically significant by the investigator.

All subjects experiencing an AE will be evaluated by the investigator and monitored until resolution of the events or until the investigator deems the event clinically stable and/or at an acceptable level. Unless the event requires hospitalization (SAE), medical treatment will be provided to the subjects at the unit and treatment medication and/or medical procedures will be provided per the treating-investigator"s clinical discretion. All clinically significant AEs, including clinically significant laboratory abnormalities, will be followed until resolution. AEs meeting the definition of SAEs require special reporting in addition to documentation in the CRDB as described below.

All AEs, including clinically significant laboratory and assessment abnormalities will be recorded according to "Common Terminology Criteria for Adverse Events" V4.0 (CTCAE) and must be recorded in the CRDB. Events occurring prior to initiation of first dose should be recorded on the Medical History page of the CRDB. Any AE occurring after initiation of first dose of study drug should be recorded on the Adverse Event page of the CRDB. AEs should be recorded in the CRDB using the medical terminology found in the source documentation. Whenever possible, diagnoses should be given when signs and symptoms are due to a common etiology. It is the investigator"s responsibility to provide his/her assessment of the relationship of the event to the study drug and the severity of the event using the following scales:

Relationship

- > Unrelated: The AE is clearly attributable to a concurrent illness, concurrent medication, clinical state, or environmental factor other than the investigative agent.
- Unlikely: The occurrence of the AE does not follow the study in a temporal sequence and/or based upon available subject information, e.g., medical history, disease process, known pharmacology of drug, a relationship between the drug and AE is unlikely.
- Possible: The AE follows a reasonable temporal sequence from the time of study drug administration, but it is possible that other factors; e.g., subject"s clinical state or concomitant mediations, environmental factors, or the drug"s pharmacology may have caused the AE.
- ➤ *Probable*: The AE follows a reasonable temporal sequence from the time of study drug administration, follows a known response pattern of the medication class, and cannot be reasonably explained by other factors.

Severity

The severity of all adverse events should be graded according to the Common Terminology Criteria for Adverse Events (CTCAE) V4.0. For those adverse events not listed in the CTCAE, the following grading system should be employed:

- ➤ *Mild* (CTCAE Grade 1): Transient symptoms, awareness of sign/symptom, but easily tolerated and no interference with subject"s daily activities
- Moderate (CTCAE Grade 2): Marked signs/symptoms that interfere with subject susual activities, but still acceptable
- > Severe (CTCAE Grade 3): Incapacitating signs/symptoms which cause considerable interference with the subject saily activities, unacceptable
- ➤ Life-threatening (CTCAE Grade 4): Life-threatening of disabling AE
- ➤ Death (CTCAE Grade 5): Death-related AE. See CTCAE Guidelines for assigning Grade 5.

Definition of Serious Adverse Event

The following definition of SAE applies for the study: "A serious AE means any AE occurring at any dose that results in any of the following outcomes: death, a life-threatening AE, inpatient hospitalization or prolongation of existing hospitalization, a persistent or significant disability/incapacity, a congenital anomaly/birth defect, or overdose of study drug. Important medical events that may not result in death, be life threatening, or require hospitalization may be considered a serious AE when, based upon appropriate medical judgment, they may jeopardize the subject or subject and may require medical or surgical intervention to prevent one of the outcomes listed in this definition. A life-threatening AE is any AE that places the subject or subject, in the view of the investigator, at immediate risk of death from the reaction as it occurred (e.g., it does not include a reaction that, had it occurred in a more severe form, might have caused death)." Reporting and Treating Serious Adverse Events as per section 17.2.

Pregnancies

Although pregnancy and lactation are not considered adverse events, it is the responsibility of investigators or their designees to report any pregnancy or lactation in a subject (spontaneously reported to them), including the pregnancy of a male subject's female partner that occurs during the trial or within 120 days of completing the trial completing the trial, or 30 days following cessation of treatment if the subject initiates new anticancer therapy, whichever is earlier. All subjects and female partners of male subjects who become pregnant must be followed to the completion/termination of the pregnancy. Pregnancy outcomes of spontaneous abortion, missed abortion, benign hydatidiform mole, blighted ovum, fetal death, intrauterine death, miscarriage and stillbirth must be reported as serious events (Important Medical Events). If the pregnancy continues to term, the outcome (health of infant) must also be reported.

Such events must be reported within 5 calendar days to the MSKCC Safety Office and within 2 working days to Merck Global Safety (Attn: Worldwide Product Safety; [contact])

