
mandatory in all patients. Pre-treatment biopsies will be obtained during fiducial placement for RT, at the time of ablation, or during a separate procedure. On treatment biopsies will be performed. 1 week after completing RT or undergoing ablation (of the radiated/ ablated lesion) and then 4 weeks after dose #1 of pembrolizumab (of a non-radiated/ ablated lesion). Tumor immunohistochemistry may be performed for PD-L1 expression and quantification of tumor infiltrating lymphocyte (TIL) subtypes, including CD8+ Tcells, CD4+ T-cells, Regulatory T-cells (Treg), and Myeloid Derived Suppressor Cells (MDSCs). Peripheral blood samples will be obtained in all patients at baseline then weeks 3, 6, and 9 for all Additional blood draws beyond week 9 are permitted based upon interesting clinic/immunological findings. Plasma may be analyzed for change in antibody responses to a broad panel of antigens (seromics). Flow cytometry may be performed for peripheral blood immune cell phenotype and their activation status, including CD8+ T-cells, CD4+ T-cells, Tregs, and MDSCs. The amount of PDL-1 expression, changes in immune cell repertoire and activation status within the tumor and peripheral blood as well as immune responses against specific tumor antigens will be correlated with clinical outcome in an exploratory manner in order to identify predictive makers for response, and to further our understanding of pembrolizumab plus RT, and pembrolizumab plus ablation in CRC.

Diagnosis and Main Criteria for Inclusion in the Study:

Inclusion Criteria

- 1. Willing and able to provide written informed consent.
- 2. Histologically- or cytologically- confirmed CRC.
- 3. Locally advanced or metastatic CRC.
- 4. Subjects have received at least two standard available therapies.
- 5. At least one tumor for which palliative RT is considered appropriate standard therapy (cohort 1); or, at least one tumor for which palliative ablation is considered appropriate standard therapy (cohort 2).
- 6. At least one index lesion that will not undergo RT or ablation, and is measurable based on RECIST 1.1.
- 7. ≥ 18 years of age on day of signing informed consent.
- 8. Consent for tumor biopsies and blood draws for research purposes.
- 9. Consent for use of available archived tissue for research purposes.
- 10. Performance status of ECOG 0 or 1.
- 11. Adequate organ function, defined as:
 - Absolute Neutrophil Count ≥ 1,500/mm³.
 - Platelet count ≥ 100,000/mm³.

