4.2 Intervention

Patients will be stratified according to eligibility for RT (cohort 1) or ablation (cohort 2). Patients in **cohort 1** will have at least one locally advanced or metastatic lesion for which palliative RT is considered appropriate standard therapy, and at least one other measurable index lesion that will not undergo RT. Patients in cohort 2 will have at least one metastatic lesion for which palliative ablation is considered appropriate standard therapy, and at least one other measurable index lesion that will not undergo ablation. Subjects in cohort 2 will undergo ablation of one or more lesions. The ablation method is at the discretion of the interventional radiologist. All subjects will undergo ablation or begin RT within 7 days prior to starting pembrolizumab. Pembrolizumab dosing may continue during RT. Subjects will receive pembrolizumab via IV infusion at 200 mg every three weeks (Q3W), and continue treatment Q3W until progression of disease, initiation of alternative cancer therapy, unacceptable toxicity, or other reasons to discontinue treatment occur, up to 24 months. Patients who had a prior response without another reason to discontinue therapy after 24 months will continue clinic visits, routine blood work (CBC, COMP, CEA) and CT/MRI every 9 weeks, and may resume treatment for an additional 12 months upon disease progression. Repeat palliative RT in cohort 1, or ablation in cohort 2, will be permitted in select cases for the treatment of isolated, non-target lesions. Patients will be evaluated by physical exam and routine blood tests every three weeks during the study period. CT or MRI will be performed during screening, and then at 9 week intervals. Tumor measurements and determination of tumor responses will be performed according to RECIST 1.1.

Subjects may continue to receive pembrolizumab beyond radiographic disease progression in the absence of clinical deterioration, and after discussion with the Principal Investigator.

All subjects will be followed up to 2 years for survival or until the study closes. Exploratory research studies to evaluate the effect of this therapy will be performed in patients using

research blood draws, and tumor biopsy at baseline, 1 week after completing RT or undergoing ablation (from the radiated/ablated lesion), and then 4 weeks after dose #1 of pembrolizumab (from a non-radiated/ablated lesion), for research purposes.

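### Non-serious events between RT or ablation and the first pembrolizumab dose are filed as medical history and would likely be missing from the combination's safety tables

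*Combined protocol and SAP*

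**What the plan says.** All references are to the combined protocol and SAP.

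- **Recording rule (Section 11.1.1).** Two consecutive sentences divide events at the first dose: "Events occurring prior to initiation of first dose should be recorded on the Medical History page of the CRDB" and "Any AE occurring after initiation of first dose of study drug should be recorded on the Adverse Event page of the CRDB". No other text assigns an event to a CRDB page, and no exception is made for RT, ablation or biopsy.
- **Timing of the local treatment.** Section 4.2: "All subjects will undergo ablation or begin RT within 7 days prior to starting pembrolizumab". Note 14 to the calendar in Section 10.0: "RT begins or ablation is performed during cycle 1, within one week prior to dose 1 of Pembrolizumab".
- **Objective (Section 2.0).** The first secondary objective concerns the safety of pembrolizumab together with RT or ablation, not of pembrolizumab alone.
- **Analysis (Section 14.0).** Recorded AEs are tabulated by organ class, term and treatment, and toxicity is summarized by cohort. Medical-history entries are not mentioned.
- **Text pointing the other way (Section 11.1.1).** Staff are to record all AEs whenever they arise during participation and to watch for "reactions to study drug and/or study procedures". On the definition of an AE: "This definition includes any abnormalities or anomalies that were not seen at baseline".
- **Serious events (Section 17.2.1).** These are reported from the signing of consent.

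**The concern.** The regimen under study begins before the AE page opens. In cohort 2 the initial ablation precedes dose 1, so its early non-serious complications can fall wholly in the medical-history period. In cohort 1 the same applies to reactions that begin in the first days of RT.

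If those entries are not carried into the Section 14.0 tables, the tables describe toxicity from dose 1 onward, under an objective that names the combination. The conflict within Section 11.1.1 also means that two staff members could file the same event on different pages, which would make the tables depend on who recorded it.

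**Working it through.** The plan states no figure on this point to reproduce. The check sets the passages side by side and adds simple arithmetic.

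**1. Length of the window.** Ablation or RT start: day −7 to day 0 relative to dose 1 (Section 4.2; calendar note 14). Adverse Event page opens: dose 1 (Section 11.1.1). Longest gap: 0 − (−7) = 7 days.

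**2. Where each kind of event goes.**

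| Event | Page under the Section 11.1.1 rule | In the Section 14.0 tables? |
|---|---|---|
| Non-serious, starts between RT/ablation and dose 1, does not recur or worsen | Medical History | Likely not: no rule brings it in |
| Starts before dose 1, recurs or worsens afterwards | Adverse Event, for the later part (worsening is within the AE definition) | Yes |
| Starts after dose 1, including reactions to RT that continues past dose 1 (allowed by Section 4.2) | Adverse Event | Yes |
| Serious, before dose 1 | Medical History, plus a report under Section 17.2.1 | Reported; tabulation not stated |

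Only the first row is a likely loss from the tables. The last is an unstated point, because expedited reporting and tabulation are different things.

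**3. Whether the calendar helps.** In the Section 10.0 calendar, as extracted from the PDF, medical history is marked at screening only, and Section 8.0 requires the history before RT or ablation. The side-effects row is first marked at week 3, not at week 0 or week 1. Section 11.1 does require AE evaluation at every visit, and week 0 is a visit with examination and vital signs. An event can therefore be elicited at week 0, but the page assigned to it does not change.

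**4. Size per affected subject.** One subject whose only event of a given term falls in the window lowers that term's rate by:
- 1/24 = 4.2 percentage points in a cohort of 24;
- 1/9 = 11.1 percentage points in a cohort of 9.

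The documents give no rate of procedural events. As an assumption only, if 5%, 10%, 20% or 30% of subjects had such an event, the expected numbers in a cohort of 24 would be 24 × 0.05 = 1.2, 24 × 0.10 = 2.4, 24 × 0.20 = 4.8 and 24 × 0.30 = 7.2.

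**5. Research biopsies (secondary).** Section 1.0 describes research biopsies as "mandatory in all patients. Pre-treatment biopsies will be obtained during fiducial placement for RT, at the time of ablation, or during a separate procedure". If done as a separate procedure, the baseline biopsy may precede dose 1 by up to 6 × 7 = 42 days (Section 8.0; calendar note 2). The next biopsy comes 7 ± 3, that is 4 to 10, days after ablation (Section 9.8.2). In cohort 2 it therefore falls between day −7 + 4 = −3 and day 0 + 10 = +10. It can precede the day of dose 1 only if ablation is on day −7, −6 or −5.

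**The case against.** The strongest case is that starting at dose 1 is deliberate. Pembrolizumab is the only named investigational drug, and Sections 5.1 to 5.3 describe ablation and RT as standard therapy. The AE definition opens with "Any untoward medical occurrence in a subject or clinical investigation subject administered a pharmaceutical product". The causality scale in Section 11.1.1 rates relationship to study drug only, and Section 17.2 collects events of clinical interest from the first dose. This is a coherent position for a drug-safety table. It does not settle the matter, because the objective names the combination, the same section extends monitoring to study procedures, and serious events are already collected from consent.

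It is also fair to say that the omission is inferred. Section 14.0 does not restrict its tables to the Adverse Event page. That stands, and is why the conclusion says likely.

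A reader might infer three stronger things, none of which the documents support:
- *That the data are lost, or that serious procedural events go unreported.* Medical-history entries stay in the CRDB, and Section 17.2.1 covers serious events from consent.
- *That the gap in the safety objective is 42 days.* A research biopsy is not part of the named combination, and this figure applies only when the baseline biopsy is a separate procedure. For RT and ablation the gap is at most 7 days. A post-ablation biopsy before dose 1 is a corner case; the calendar marks that biopsy at week 1.
- *That a trial decision is biased.* Safety is descriptive, and Section 14.0 sets no AE threshold. The safety criterion in Section 9.7 concerns adverse drug reactions and gives no number.

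**Conclusion.** The point holds in limited form. Followed as written, the page rule in Section 11.1.1, read with Section 14.0, would likely leave non-serious events that start in the period of up to 7 days between RT or ablation and dose 1, and do not recur or worsen, out of the by-cohort AE tables. The effect is mainly in cohort 2. It rests on two assumptions: that sites follow the specific page rule over the general instruction to record all AEs, and that tabulated AEs are those on the Adverse Event page. Each affected subject is worth 4.2 or 11.1 percentage points for a term; how many there would be cannot be derived.

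Not affected: the primary endpoint, the sample size, expedited serious-event reporting, and events that start or worsen after dose 1. Priority is minor to moderate, because no decision threshold depends on these tables.

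**What to change.** - **Section 11.1.1.** Reconcile the page rule with the instruction to record all AEs and monitor reactions to procedures, so that AEs go on the Adverse Event page from the start of RT or ablation. As a secondary point, record events attributed to a research biopsy there from the time of that biopsy. Limiting this to attributed events avoids up to 6 weeks of unrelated entries. It needs a procedure attribution on the CRF, since the present scale covers study drug only.
- **Section 14.0.** State that these events, including pre-dose serious events, are tabulated by cohort and split by onset before or after dose 1. Use subjects who started RT or ablation as the denominator for the pre-dose part, and subjects who received pembrolizumab for the post-dose part. A biopsy event in a subject who never starts RT or ablation falls outside both and can be listed.
- **Section 10.0 calendar.** Mark side-effect reporting at the existing week 0 visit.

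The cost is protocol wording, a CRF instruction and one calendar mark, with no added visit. There will be somewhat more AE entries and slightly higher reported AE rates. The split by onset keeps the view from the first pembrolizumab dose.
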